11.3.1 Analysis of Key Study Endpoints

11.3.1.1 Efficacy Analysis

Primary Endpoint

The primary efficacy endpoint is hepatic histological improvement in NAS (NASH CRN scoring). A responder (subjects with hepatic histological improvement) is defined as having all of followings:

- (1) At least 2 point reduction in NAS at 12 months. The reduction in NAS must also include at least a 1 point reduction in either ballooning or inflammation.
- (2) No worsening of fibrosis, defined as no increase in CRN fibrosis score.

Each MSDC-0602K dose group will be compared with the placebo group at the two-sided 0.05 significance level. For each comparison, the null hypothesis is that there is no difference in response rates between the MSDC-0602K dose and placebo. The alternative hypothesis is that there is a difference in response rates between the MSDC-0602K dose and placebo. The primary analysis of the primary efficacy endpoint will be performed in the mITT, with supportive analysis

in the PPS. The number and percentage of responders will be summarized by treatment group. The primary analysis will be conducted using observed data included in the analysis dataset. Sensitivity analyses will be conducted where missing values are multiply imputed, and where subjects with missing data will be treated as non-responders. Comparisons between each active treatment group and the placebo group will be evaluated using appropriate contrasts from a logistic regression model that includes adjustments for the randomization stratification factors (presence of diabetes mellitus, Vitamin E use ≥ 400 IU, and baseline fibrosis 1 versus ≥ 2) and baseline NAS. Model-adjusted odds ratios for each active dose group relative to placebo and their associated 95% confidence intervals (CIs) will be provided. In addition, stratification-adjusted differences in response rates between each active dose group and placebo and their associated 95% CIs will be provided.

Supportive analyses of the primary endpoint will include comparisons of each active dose group with placebo using Cochran-Mantel-Haenszel (CMH) tests adjusting for the randomization stratification factors. Sensitivity analysis for primary endpoint will be performed using a logistic regression model adjusting for treatment, gender, presence of diabetes mellitus, Vitamin E use ≥ 400 IU, baseline fibrosis and baseline NAS. Adjusted odds ratios relative to placebo and the corresponding 95% CIs and p-values will be provided.

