6.2.3 Imputation for Primary Endpoint

Sensitivity analyses will be performed on the primary endpoint using two different imputation methods. The sensitivity analyses will include all subjects who were randomized and who received at least one dose of study drug. Two approaches will be used to impute or substitute missing response at 12 months. Post-baseline observations that have been excluded from the primary analysis due to biopsies taken more than 14 days after last dose of study drug will be treated as missing and imputed or substituted as well.

When using multiple imputation, missing baseline and/or post-baseline values needed to determine response at 12 months will be imputed multiple times to account for the uncertainty about the true values to impute. To this end, each of the four categorical variables underlying the response definition of the primary endpoint will be imputed if missing, using the following categories:

- Steatosis: 0, 1, 2, 3
- Lobular inflammation: 0, 1, 2, 3
- Ballooning: 0, 1, 2
- Fibrosis score: 0, 1, 2, 3, 4

Using the SAS[®] procedure PROC MI 10 imputed data sets will be generated. The regression model will be adjusted for the corresponding baseline values and will further use presence of diabetes mellitus, Vitamin E use ≥ 400 IU, age, and sex as covariates.

An example of the SAS[®] code to be used is below:

```
proc mi data= out=<output dataset> seed=1234 nimpute=10
  minimum=<...> maximum=<...> round=<...>;
var <12 months steatosis> <baseline steatosis>
  <12 months lobular inflammation> <baseline lobular inflammation>
  <12 months ballooning> <baseline ballooning>
  <12 months fibrosis score> <baseline fibrosis score>
  <presence of diabetes mellitus> <Vitamin E use  $\geq 400$  IU> <sex><age at baseline>;
run;
```

The 10 multiple imputed datasets will be used separately in the statistical analysis model and the resulting odds ratios and 95% CIs will be combined via Rubin's rules (using PROC MIANALYZE) to provide a global estimate of the odds ratio with a corresponding 95% CI and p-value.

As a second sensitivity analysis of the primary endpoint, subjects with missing response data at 12 months will be included as non-responders. Similar to above, this sensitivity analysis will include all subjects who were randomized and who received at least one dose of study drug.

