6.2.4 Imputation for Missing Changes in Laboratory Values

HbA1c

Additional sensitivity analyses may be performed conditional on the distribution of changes in glycemic control medications between the placebo and active treatment groups at 6 and 12 months.

If more than 35% of the subjects who had a major up-titration of glycemic control medications are in the placebo group, a sensitivity analysis may be done where the 6- and 12-month values of HbA1c for subjects who had a major up-titration of glycemic control medications will be imputed to be 0.5 % higher than the observed value.

If more than 15% of the subjects who had a major down-titration of glycemetic control medications are in the placebo group, a sensitivity analysis may be done where the 6- and 12-month values of HbA1c for subjects who had a major down-titration of glycemetic control medications will be imputed to be 0.5 % lower than the observed value.

If more than 35% of the subjects missing paired change-from-baseline values of HbA1c (separately at 6 and 12 months) are in the placebo group, a sensitivity analysis may be performed where the missing follow-up value will be assigned the baseline value plus 0.5%.

Liver function tests and other markers

Additional sensitivity analyses may be performed conditional on the distribution of missing values between the placebo and active treatment groups at 6 and 12 months.

If > 35% of the subjects missing paired change-from-baseline values of the following laboratory tests (separately at 6 and 12 months) are in the placebo group, a sensitivity analysis may be performed where missing follow-up values will be assigned the corresponding baseline values plus 0.5 times the maximum change (maximum increase) from baseline for the parameter observed in any subject (i.e., regardless of treatment group) at the timepoint: ALT, AST, ALP, Total Bilirubin, GGT, pro thrombin time, APRI score, CK-18, ELF, FIB-4, Pro-C3, Fibro-test score, and HOMA-IR. Likewise for albumin, missing follow-up values may be assigned the corresponding baseline values minus 0.5 times the minimum change (maximum decrease) from baseline .

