7.8 Efficacy

7.8.1 Primary Efficacy Analysis

The primary efficacy endpoint is hepatic histological improvement in NAS (NASH CRN scoring). A responder (subjects with hepatic histological improvement) is defined as having all of following:

- A decrease of at least 2 points in NAS at 12 months. The reduction in NAS must also include at least a 1 point reduction in either ballooning or inflammation.
- No worsening of fibrosis, defined as no increase in CRN fibrosis score of ≥ 1 stage.

Each MSDC-0602K dose group will be compared with the placebo group at the two-sided 0.05 significance level. For each comparison, the null hypothesis is that there is no difference in response rates between the MSDC-0602K dose and placebo. The alternative hypothesis is that there is a difference in response rates between the MSDC-0602K dose and placebo. The primary analysis of the primary efficacy endpoint will be performed in the mITT population, with supportive analysis in the PPS population. The number and percentage of responders will be summarized by treatment group. Analyses of liver biopsy findings will be based on the central expert histopathologist's repeat read of the Screening biopsy and read of the Visit 7 biopsy. The central read of the Screening biopsy for purposes of determining subject eligibility, and the local pathologist's assessments, will not be considered for these analyses. Covariate adjustment for randomization stratification factors diabetes mellitus, baseline fibrosis (F1 versus F2/F3), and vitamin E use will utilize values reported at randomization and which determined the stratum in which the subject was randomized.

The primary analysis will be conducted using observed data included in the analysis dataset. Five additional sensitivity analyses will be conducted in the mITT population where (1) missing values are multiply imputed, (2) subjects with missing data will be treated as non-responders, as outlined in Section 6.2.3, (3) subjects with biopsy results up to and including (\leq) 1 day after last dose of study drug will be included, (4) subjects with biopsy results up to ($<$) 7 days after last dose of study drug will be included, and (5) all observed data will be used (including biopsy results obtained more than 14 days after last dose of study drug). These sensitivity analyses will include all subjects who were randomized and who received at least one dose of study drug.

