Comparisons between each active treatment group and the placebo group will be evaluated using appropriate contrasts from a logistic regression model including treatment and adjusted for presence of diabetes mellitus, baseline fibrosis F1 versus F2/F3, and ordinal baseline NAS. Model-adjusted odds ratios for each active dose group relative to placebo and their associated 95% confidence intervals (CIs) and p-values will be provided.

In addition, stratification-adjusted differences in response rates (risk differences) adjusted for presence of diabetes mellitus, baseline fibrosis F1 versus F2/F3, and ordinal baseline NAS between each active dose group and placebo and their associated 95% CIs and p-values will be provided (LaVange et al 2005; Zink and Koch 2012).

Statistical Analysis Plan

Version: Final 1.5

Date of Issue: 16-May-2019

Cirius Protocol No. MSDC-0602K-C009NASH

Supportive analyses of the primary endpoint will include comparisons of each active dose group with placebo using Cochran-Mantel-Haenszel (CMH) tests stratified by presence of diabetes mellitus.

Sensitivity analysis for the primary endpoint will be performed using a logistic regression model including treatment and adjusting for presence of diabetes mellitus, baseline fibrosis F1 versus F2/F3, sex, age, and ordinal baseline NAS. Adjusted odds ratios relative to placebo and the corresponding 95% CIs and p-values will be provided.

A summary of the planned primary efficacy analyses is given below:

Method	mITT Observed data	PPS Observed data, data exclusions possible due to non-compliance	mITT Multiply imputed response data	mITT Missing response status at 12 months set to non-responder	mITT Observed data ≤1 day after last dose of study treatment	mITT Observed data <7 days after last dose of study treatment	mITT Observed data including results any time after last dose of study treatment
Logistic regression (odds ratios) including treatment group and adjusted for presence of diabetes mellitus, baseline fibrosis F1 versus F2/F3, ordinal baseline NAS.	X*	X	X	X	X	X	X
Stratification-adjusted differences in response rates (risk differences) between each active dose group and placebo adjusted for presence of diabetes mellitus, baseline fibrosis F1 versus F2/F3, ordinal baseline NAS.	X	X	X	X	X	X	X
CMH tests of each active dose group versus placebo stratified by presence of diabetes mellitus.	X	X					

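### The multiple-imputation model for the primary endpoint omits treatment group, so missing responses are drawn from all four arms pooled and the treatment difference is distorted, usually toward zero

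*SAP*

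**What the plan says.** Protocol Section 11.3.1.1 gives no imputation model. It says only "Sensitivity analyses will be conducted where missing values are multiply imputed", alongside a non-responder analysis.

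The model is in SAP Section 6.2.3. The 12-month and baseline steatosis, inflammation, ballooning and fibrosis scores are imputed 10 times. On covariates the text reads "The regression model will be adjusted for the corresponding baseline values and will further use presence of diabetes mellitus", followed by Vitamin E use, age and sex. The example PROC MI call lists the same variables in one VAR statement that ends "<sex><age at baseline>". It has no treatment variable and no BY statement. The same section widens the set to be imputed: "biopsies taken more than 14 days after last dose of study drug will be treated as missing and imputed or substituted as well".

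SAP Section 7.8.1 makes this the first of five added mITT sensitivity analyses and refers back for the details: "1) missing values are multiply imputed, (2) subjects with missing data will be treated as non-responders, as outlined in Section 6.2.3". The imputed data sets then go into models that estimate treatment effects. One uses "appropriate contrasts from a logistic regression model including treatment and adjusted for presence of diabetes mellitus", with baseline fibrosis and NAS. The summary table also applies to the imputed data the row "Stratification-adjusted differences in response rates (risk differences) between each active dose group and placebo adjusted for presence of diabetes mellitus". SAP Section 8, which lists changes from the protocol, does not mention imputation by arm or a deliberate choice to pool.

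**The concern.** The imputation model is poorer than the analysis model in the one term that matters most. Randomization balances the baseline scores, diabetes, Vitamin E use, age and sex across arms, so none of them can stand in for treatment. A placebo subject and a 250 mg subject with the same baseline profile and no 12-month biopsy receive draws from the same distribution. Imputed subjects then add close to zero treatment difference, which dilutes the difference seen in the observed subjects.

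Nothing in the plan makes a decision depend on this analysis. It is, however, the only one of the five added mITT analyses that models the missing responses; the others assign non-response or change the biopsy window. Its job is to show whether missing data matter. As specified, a gap between it and the primary result mixes the effect of the missing data with the effect of the omitted term, and the analysis itself does not separate them.

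**Working it through.** **Inputs.** SAP Section 2.3: 20% placebo, 39.5% active, two-sided 0.05, 85 evaluable per arm, 10% not completing the 12-month assessment, 380 randomized. SAP Section 2.2: 1:1:1:1 allocation, so 95 per arm. SAP Section 6.2.3: 10 imputations.

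**The plan's own figure.** With the pooled-variance normal approximation and mean rate (0.20 + 0.395)/2 = 0.2975:

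- Null SE = √(2 × 0.2975 × 0.7025 / 85) = 0.0701.
- Alternative SE = √((0.20 × 0.80 + 0.395 × 0.605) / 85) = 0.0685.
- z = (0.195 − 1.96 × 0.0701)/0.0685 = 0.84, so power is 80.0%.
- 340/0.9 = 378, rounded in the plan to 380.

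The stated power and sample size reproduce.

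**Expected rates under pooled imputation.** If arm k has true rate p_k and missing fraction m_k, and data are missing at random within arm, the expected rate after imputation is

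q_k = (1 − m_k) p_k + m_k P,

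where P is the observed response rate over all four arms. With equal missingness m, the P terms cancel and the difference is (1 − m)(p_active − p_placebo).

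All three doses at 39.5%: P = (20 + 3 × 39.5)/4 = 34.6%. At m = 10%, placebo is 0.9 × 20 + 0.1 × 34.6 = 21.46% and active is 0.9 × 39.5 + 0.1 × 34.6 = 39.01%.

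| Scenario | Placebo | Dose | Difference (points) | OR |
|---|---|---|---|---|
| No missing data | 20% | 39.5% | 19.5 | 2.61 |
| 10% missing, all doses active | 21.46% | 39.01% | 17.55 | 2.34 |
| 10% missing, one dose active (P = 24.9%) | 20.49% | 38.04% | 17.55 | 2.38 |
| 15% missing (assumed), all active | 22.19% | 38.77% | 16.6 | 2.22 |
| 20% missing (assumed), all active | 22.93% | 38.53% | 15.6 | 2.11 |

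The 15% and 20% rows are included because late biopsies count as missing on top of dropout.

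**Unequal missingness.** SAP Section 6.2.4 foresees this for laboratory values, with analyses "conditional on the distribution of missing values between the placebo and active treatment groups". Borrowing its 35%-in-placebo trigger as an illustration, with 38 of 380 missing: placebo 13.3/95 = 14.0%, each dose 24.7/285 = 8.7%. With all doses active this gives 22.08% versus 39.10%, a difference of 17.0 points, OR 2.27.

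The bias can also run the other way. Assume true rates 20/20/39.5/39.5% with 5/15/10/10% missing. Then P = 29.75%, placebo becomes 20.49% and the inactive dose 21.46%. A dose with no effect gains about 1.0 point (OR 1.06).

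**Simulation at the planned rates.** 6,000 trials, 95 per arm, binary response missing completely at random, 10 imputations, Rubin's rules on the log OR, no covariates. Each cell gives the chance of p<0.05 for one dose versus placebo.

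| Setting | Observed data | Imputed without treatment | Imputed with treatment |
|---|---|---|---|
| 10% missing, all active | 80.1% | 71.8% | 79.2% |
| 20% missing, all active | 75.9% | 55.9% | 74.9% |
| 10% missing, one active | 80.2% | 73.6% | 79.8% |

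In the first row, 10.5% of trials significant on observed data lose significance when treatment is left out, against 2.3% when it is in. The mean differences are 19.49, 17.55 and 19.47 points. Repeat runs with slightly different implementations put the 71.8% figure between 71.6% and 73.7%, and the 10.5% figure between 8.8% and 10.5%.

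**Closer to the SAP's method.** A second simulation (1,500 trials) imputed the four scores under a joint normal model with bounds and rounding, using assumed score distributions that give about 25% versus 45% response. At 10% missing the differences were 19.3 (observed), 17.4 (without treatment) and 19.1 (with treatment). At 20% they were 19.4, 15.5 and 19.0. Because the score distributions are assumed, this supports the direction and rough size only.

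**The case against.** The best argument for pooling is that it may be nearer the truth. Many of the subjects to be imputed stopped drug early or were biopsied more than 14 days after the last dose. If missing subjects in every arm respond at 20%, the true all-subject rates are 20% and 0.9 × 39.5 + 0.1 × 20 = 37.55%, a difference of 17.55 points (OR 2.41). Pooled imputation then gets the difference right, and imputation by arm overstates it by about 2 points. Section 6.2.4 also contains a laboratory-value rule that uses the largest change seen in any arm, so a conservative pooled choice is credible. This stands as far as it goes: which model is better depends on the assumption. But the SAP states no such assumption, the laboratory rule does not cover histology, and the inactive-dose example shows that pooling is not reliably conservative.

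Second, this is a sensitivity analysis with no p<0.05 rule attached, and the shift at 10% missing is 1.95 points. That is correct and limits the importance of the point. The significance figures describe the size of the distortion, not a decision error.

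Third, non-responder imputation with equal missingness also gives 17.55 points (18.0% versus 35.55%, OR 2.51), so shrinkage is not peculiar to pooling. True, but non-responder imputation declares its assumption openly.

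Fourth, disposition by arm, the non-responder analysis and the all-observed analysis would help a reader judge the pooling effect. They would allow an approximation after the fact; they do not make the imputation analysis interpretable by itself.

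**Conclusion.** The concern holds. Treatment is absent from both the covariate sentence and the example code, and no other section supplies it or declares pooling intentional. Under missing at random within arm and equal missingness, the expected risk difference falls by the missing fraction: 19.5 to 17.55 points at the planned 10%, and to 15.6 at an assumed 20%. With unequal missingness the direction is not fixed.

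Three limits apply. The factor (1 − m) is for missing 12-month biopsies; a subject missing only the baseline reread still has 12-month scores that carry some arm information. The calculations approximate PROC MI rather than reproduce it. And if dropouts respond alike across arms, the smaller difference is not a bias. The primary analysis is untouched, so this should be fixed but does not threaten the main result.

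**What to change.** Add treatment group to the covariate sentence in SAP Section 6.2.3 and to the PROC MI variable list, or impute separately by randomized arm. The example code has no CLASS statement, so treatment should enter as indicators for the three doses; a single numeric code would impose a linear pattern across the arms.

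If pooling is meant as a conservative assumption about dropouts, state that and run a version with treatment beside it.

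The corrected analysis will lie close to the observed-data result, because the imputation model uses no intermediate post-baseline predictors. It is therefore a weak stress test, and non-responder imputation remains the harder one.

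The cost is a few lines of SAP text and code, with no extra data and no burden on subjects. The documents do not show whether database lock was still pending when SAP Final 1.5 was issued. If unblinding has already happened, report the version with treatment next to the planned one and label it as added later.

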7.5 Efficacy and Pharmacokinetic Assessments

For all subjects, blood samples for pharmacologic (efficacy and safety) assessments will be drawn at all visits except Screening (Table 1). All blood samples should be drawn in a fasted state (approximately 10 hours). Instructions for collecting, processing, storing and shipping of blood samples for pharmacologic and pharmacokinetic analyses will be provided in the Laboratory Manual.

Blood samples for trough PK analysis of MSDC-0602 and MSDC-0597 will be collected pre-dose at Study Visits 2, 4, 5, 6 and 7 (Days 30, 90, 180, 270 and 360).

Blood samples for analysis of FPG and HbA1c will be collected at Screening.

Blood samples for analysis of insulin, HOMA-IR, FPG, HbA1c, TG, FFA and fasting cholesterol (total, HDL, LDL, VLDL) will be collected as part of the standard chemistry profile at Study Visits 1, 5, and 7 (Days 1, 180 and 360).

Blood samples for analysis of liver function tests (AST, ALT, bilirubin, PT/INR, ALP, GGT and albumin) will be collected at Study Visits 1, 2, 3, 4, 5, 6 and 7 (Days 1, 30, 60, 90, 180, 270 and 360).

Blood samples for analysis of HMW adiponectin, hsCRP, osteocalcin, serum CTX concentrations will be collected at Study Visits 1, 5, and 7 (Days 1, 180, and 360).

Blood samples for biomarkers of liver apoptosis (CK-18 [M30 and M65]) will be collected at Visits 1, 5 and 7 (Days 1, 180, and 360), whereas blood samples for TIMP-1, PIIINP, HA will be collected at Visits 1 and 7 (Days 1 and 360).

Serum samples for NMR analysis of lipoprotein particle size will be collected at Study Visits 1 and 7 (Days 1 and 360).

Blood samples will be collected at Visit 1 (Day 1) to be analyzed for genotyping.

Plasma samples for future miRNA measurements and additional biomarkers of interest will be collected at Study Visits 1, 5 and 7 (Days 1, 180 and 360).

Data obtained from the circulating liver function tests and other biomarkers will be used to calculate composite scores that may provide an indirect measure of changes in fibrosis from baseline to the 12 month endpoint (Days 1 and 360).

It is estimated that approximately 226 mL of blood for the safety, pharmacokinetic, and pharmacodynamic parameters will be drawn from each subject who completes the trial.

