11.1 Sample Size and Power Calculations

Each active treatment group will be compared with the placebo group at the two-sided 0.05 significance level; 85 subjects per arm provides approximately 80% power to detect a difference in the proportions of subjects achieving the primary efficacy endpoint of 39.5% in any MSDC-0602K group versus 20% response rate in the placebo group. These response rates are similar to effects reported after 18 months daily treatment with 45 mg pioglitazone (58% response) or placebo (17% response) in subjects with pre-diabetes or T2DM (32); after 96 weeks daily treatment with 30 mg pioglitazone (34% response) or placebo (19%) in non-diabetic adults with NASH in the PIVENS study (34); and in the GOLDEN study, after 52 weeks daily treatment with 120 mg elafibranor (32% response) or placebo (21%) in the subset of NASH subjects with a baseline NAS ≥ 4 (35). Assuming 10% of subjects will not complete the 12-month assessment due to early dropout, 380 subjects will be randomized to the study.

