2.2 Overall Study Design

This is a randomized, double-blinded, placebo-controlled multiple-dose phase II study to evaluate the safety, tolerability and efficacy of three dose levels of MSDC-0602K in subjects with non-alcoholic steatohepatitis (NASH).

Approximately 380 subjects will be randomized at 1:1:1:1 ratio to the following four treatment arms, and the drug is taken orally once per day for 12 months:

- MSDC-0602K 62.5 mg
- MSDC-0602K 125 mg
- MSDC-0602K 250 mg
- Placebo

Randomization will be stratified by:

- Presence of Type 2 diabetes mellitus (T2DM) (Yes/No)
- Use of Vitamin E \geq 400 IU (Yes/No)
- Fibrosis score (F1 vs. F2/F3)

This study will comprise a maximum 42-day Screening period, a treatment period of 360 days and a 14-day follow-up period. The total duration of the study for each subject will be up to 416 days, including follow-up.

The primary efficacy endpoint will be assessed at 12 months after randomization. Visits to the clinic will be at baseline, 1, 2, 3, 6, 9, and 12 months, with one follow-up visit at study day 374.

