2.3 Sample Size and Power

Each active treatment group will be compared with the placebo group at the two-sided 0.05 significance level; 85 subjects per arm provides approximately 80% power to detect a difference in the proportions of subjects achieving the primary efficacy endpoint of 39.5% in any MSDC-0602K group versus 20% response rate in the placebo group. These response rates are similar to effects reported after 18 months daily treatment with 45 mg pioglitazone (58% response) or placebo (17% response) in subjects with pre-diabetes or T2DM (Cusi 2014); after 96 weeks daily treatment with 30 mg pioglitazone (34% response) or placebo (19%) in non-diabetic adults with NASH in the PIVENS study (Sanyal 2010); and in the GOLDEN study, after 52 weeks daily

treatment with 120 mg elafibranor (32% response) or placebo (21%) in the subset of NASH subjects with a baseline NAS ≥ 4 (Ratziu 2016). Assuming 10% of subjects will not complete the 12-month assessment due to early dropout, 380 subjects will be randomized to the study. Sample size calculations were made using nQuery Advisor® (Statistical Solutions Ltd., Boston, MA, USA).

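### The multiple imputation of the primary endpoint omits randomized treatment and all on-treatment data, so it shrinks the dose-placebo difference and cannot correct for response-related dropout

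*SAP*

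**What the plan says.** The primary analysis uses only subjects with usable month-12 histology (SAP 7.8.1): "The primary analysis will be conducted using observed data included in the analysis dataset". Multiple imputation is the first of five sensitivity analyses listed there.

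SAP 6.2.3 imputes four month-12 scores: steatosis, lobular inflammation, ballooning and fibrosis. On predictors it says: "The regression model will be adjusted for the corresponding baseline values and will further use presence of diabetes mellitus", followed by Vitamin E use, age and sex. The example PROC MI call lists the baseline and month-12 scores and these covariates. It has no treatment variable and no BY-treatment step. The analysis model applied to the imputed data (SAP 7.8.1) does contain treatment.

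The trial collects much more between baseline and month 12:

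- Liver tests at every treatment visit (Protocol 7.5): "Blood samples for analysis of liver function tests (AST, ALT, bilirubin, PT/INR, ALP, GGT and albumin) will be collected at Study Visits" 1 to 7.
- Body weight at all study visits (Protocol 7.2).
- CK-18 and HbA1c at month 6 (Protocol 7.5).
- Pro-C3 at month 6 (Protocol Table 1 and 6.2.7).

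None of these enters the imputation.

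**The concern.** Two things are missing from the imputation model, and they act differently.

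**Treatment.** If the model does not know the arm, a subject lost from a dose group receives scores typical of the whole trial, and so does a subject lost from placebo. Each arm is pulled toward the common average.

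**On-treatment data.** When there is no biopsy, all four month-12 scores are normally absent together, so the other month-12 scores in the variable list give no help. The prediction then rests on baseline alone and cannot tell a dropout whose ALT was falling from one whose ALT was rising.

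The protocol makes the second gap relevant. Sections 6.4 and 6.5 link stopping study drug to HbA1c and to AST, ALT or bilirubin. SAP 5.2 generally restricts assessments to 14 days after the last dose, and SAP 6.2.3 treats later biopsies as missing. A subject who stops early on these grounds can therefore become a missing case although the relevant laboratory values are on file. At stake is whether this sensitivity analysis tests the observed-data result against informative dropout at all.

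**Working it through.** **1. The plan's own figures.** SAP 2.3 tests each dose against placebo at a two-sided level of 0.05. On power it states: "85 subjects per arm provides approximately 80% power to detect a difference in the proportions of subjects". The planning rates are 39.5% for any dose, set against the placebo rate: "group versus 20% response rate in the placebo group". Protocol 11.1: "Assuming 10% of subjects will not complete the 12-month assessment due to early dropout, 380 subjects will be randomized to the study". SAP 2.2: "Approximately 380 subjects will be randomized at 1:1:1:1 ratio to the following four treatment arms".

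With n = 85, p0 = 0.20, p1 = 0.395 and mean rate 0.2975:

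- Null SE = sqrt(2 x 0.2975 x 0.7025 / 85) = 0.0701.
- Alternative SE = sqrt((0.20 x 0.80 + 0.395 x 0.605) / 85) = 0.0685.
- Power = Phi((0.195 - 1.96 x 0.0701) / 0.0685) = Phi(0.84) = 80.0%, as stated.
- 340 / 0.90 = 378, against 380 stated.

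**2. Leaving out treatment.** Let a fraction m be missing at random in every arm, and let imputed responders follow the all-arm rate P. Each arm becomes (1 - m) x p + m x P. P cancels in the difference, which becomes (1 - m) x (p1 - p0).

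- All three doses work: P = (0.20 + 3 x 0.395) / 4 = 0.346. At m = 0.10, placebo is 0.180 + 0.0346 = 21.5% and active is 0.3555 + 0.0346 = 39.0%.
- One dose works: P = (3 x 0.20 + 0.395) / 4 = 0.249. Placebo is 20.5% and active 38.0%.

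| Missing per arm | Difference, points | Odds ratio, three doses work | Odds ratio, one dose works |
|---|---|---|---|
| 0 | 19.5 | 2.61 | 2.61 |
| 10% | 17.55 | 2.34 | 2.38 |
| 20% | 15.6 | 2.11 | 2.17 |
| 25% | 14.6 | 2.00 | 2.07 |

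Non-responder imputation with equal missingness gives the same factor, (1 - m).

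**3. Imputing the four scores.** Rows A to C come from 600 simulated trials: four arms of 95, multivariate-normal imputation with rounding and clipping, 10 imputations, rates about 21% and 39%. Rows D to F are further simulated settings; r is the assumed marker-histology correlation. Entries are dose-placebo differences in points; a dash means no figure is available.

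| Setting | Full data | Complete case | SAP model | + treatment | + treatment + marker | + marker, no treatment |
|---|---|---|---|---|---|---|
| A. 10% random | 18.2 | 18.3 | 16.4 | 18.0 | 18.0 | 16.8 |
| B. 20% random | 18.5 | 18.5 | 14.9 | 18.0 | 18.0 | 15.7 |
| C. Active-arm dropout follows on-treatment ALT, about 18% missing | 18.4 | 21.1 | 17.3 | 20.7 | 18.2 | 16.0 |
| D. 15% random | 19.1 | 19.1 | 16.2 | - | - | - |
| E. Active-arm dropout follows marker, r = 0.4 | 19.4 | - | 18.8 | - | 19.6 | 17.2 |
| F. Placebo dropout follows marker, r = 0.7 | 18.9 | 16.1 | - | 16.2 | 18.9 | - |

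Row B agrees with step 2: 0.80 x 18.5 = 14.8, against 14.9 simulated. In row C the SAP model falls nearer the full-data value than complete case does, but only because an upward dropout bias and the downward shrinkage partly offset.

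**4. Treatment in the model, baseline predictors only.** Here the binary response was imputed by logistic regression: 1,200 replicates, 95 per arm, 11% to 16% missing. Entries are bias in points.

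| Dropout mechanism | r | Complete case | Baseline + treatment | + month-6 marker |
|---|---|---|---|---|
| Placebo follows poor marker, active does not | 0.4 | -1.13 | -1.20 | -0.07 |
| Same | 0.75 | -1.94 | -1.98 | -0.03 |
| Placebo and active run opposite ways | 0.4 | -2.41 | -2.47 | -0.10 |
| Same | 0.75 | -4.41 | -4.41 | -0.05 |

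Baseline plus treatment stays within 0.1 point of complete case. Row C shows the opposite sign: 20.7 - 18.4 = +2.3 with treatment added, and 21.1 - 18.4 = +2.7 for complete case.

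**The case against.** The imputation is one of five sensitivity analyses, and the primary result does not depend on it. Non-responder imputation and an analysis of all observed biopsies are also planned, and subjects who stop drug are meant to continue visits, so some will still supply a biopsy. This stands and limits the weight of the point. But non-responder imputation assigns one fixed outcome, the all-biopsy analysis recovers only biopsies that were taken, and neither uses on-treatment data.

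The code is labelled an example, so a programmer might add treatment. The covariate sentence omits it too, so the plan does not require that.

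The bias sizes are assumed and partly circular: dropout was generated from the same marker that then corrects it, so near-complete recovery is a best case. Against a standard error of about 6.9 points at 85 per arm, -1.1 to -2.0 points is 0.16 to 0.29 standard errors. This also stands.

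A reader might infer that the imputation as written merely repeats the complete-case analysis, because its covariates resemble those of the analysis model. The documents do not support that: treatment is in the analysis model and absent from the imputation model, so the planned result shrinks. The near-repetition appears only after treatment alone is added.

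A reader might also infer that useful data exist for every dropout. Those leaving before Visit 2 have no scheduled on-treatment values, and those leaving before Visit 5 have no month-6 biomarkers.

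**Conclusion.** The point holds as two linked gaps in SAP 6.2.3. Leaving out treatment shrinks the difference by about the missing fraction: 19.5 to about 17.6 points at 10% missing, assuming equal random missingness and no covariate imbalance. Adding treatment alone leaves an analysis that cannot correct for dropout linked to on-treatment response. The illustrative bias is about 1 to 4 points and can go either way. It depends on assumed dropout mechanisms, correlations (0.4 to 0.75 in step 4) and 11% to 18% missing. The 20% and 25% rows of step 2 also go beyond the 10% in the documents.

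The two gaps must be closed together. With active-arm dropout driven by the marker, adding it without treatment moved the estimate further from the full-data value: 17.3 to 16.0 against 18.4, and 18.8 to 17.2 against 19.4. This is a worthwhile, inexpensive correction to a sensitivity analysis. It is not a defect in the primary analysis.

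**What to change.** In SAP 6.2.3, before unblinding for the final analysis:

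- Add randomized treatment, as a class variable or by imputing within arm.
- Add with it a short auxiliary list fixed by name: log ALT and log AST at months 3, 6 and 9, weight at month 6, and Pro-C3 at month 6.
- State that the auxiliaries are not to be used without treatment.
- Change the example code to match the text.

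Pro-C3 is a safer choice than ELF. Protocol 7.5 lists the ELF components only at Visits 1 and 7, while Table 1 and Protocol 6.2.7 place ELF at Visit 5.

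The analysis model and the observed-data primary analysis stay unchanged. The cost is SAP wording and a longer variable list; no new data are needed. Some auxiliaries will themselves be missing and must be imputed jointly, and the earliest dropouts will contribute no auxiliary information.
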